### **3.3. SUBJECT POPULATION**

Eighteen (18) evaluable subjects with ALS meeting the following study entry criteria will be enrolled.

---

### 3.3.1. INCLUSION CRITERIA

---

Subjects must satisfy all of the following criteria to be included in the study:

1. Age  $\geq$  21 years, but  $\leq$  75 years
2. Subjects diagnosed with:
  - clinically definite ALS,
  - clinically probable ALS, or
  - clinically probable-laboratory supported ALS;as specified in the revised El Escorial / Airlie House diagnostic criteria
3. Onset of ALS  $<$  2 years at Screening;
4. Forced Vital Capacity (FVC)  $\geq$  60% of predicted;
5. Revised Amyotrophic Lateral Sclerosis Functional Rating Scale (ALSFRS-R)  $\geq$  30;
6. Not taking riluzole, or on a stable dose for at least thirty days prior to Screening (defined as no noted toxicities);
7. Able and willing to give informed consent;
8. If female of childbearing potential, negative urine pregnancy test at Screening and using acceptable method of birth control during the study.

### 3.3.2. EXCLUSION CRITERIA

---

Subjects *will not be eligible for the study* if any of the following criteria are present:

1. Neurological symptom(s) due to vitamin B12 deficiency;
2. Requires tracheotomy ventilation or noninvasive ventilation  $>$  16 hours / day;
3. Comorbidities such as Parkinson's disease, schizophrenia, renal failure, or any other severe complication that, in the Investigator's opinion, will compromise the safety of the patient or confound interpretation of the data collected in this study;
4. Other neuromuscular disease;
5. Inflammatory disorder of the blood vessels (inflammatory angiopathy, such as Buerger's disease);
6. Active infection;
7. Chronic inflammatory disease (e.g., Crohn's disease, rheumatoid arthritis);
8. Positive HIV or HTLV at Screening;
9. Active Hepatitis B or C as determined by Hepatitis B core antibody (HBcAb), antibody to Hepatitis B surface antigen (IgG and IgM; HBsAb), Hepatitis B surface antigen (HBsAg) and Hepatitis C antibodies (Anti-HCV) at Screening;
10. Subjects with known immunosuppression or currently receiving immunosuppressive drugs, chemotherapy or radiation therapy;
11. Stroke or myocardial infarction within last 3 months;
12. Patients with a recent history ( $<$  5 years) of malignant neoplasm except basal cell carcinoma or squamous cell carcinoma of the skin (if excised and no evidence of recurrence);

- 
13. Subjects requiring > 81 mg daily of acetylsalicylic acid; subjects may be enrolled if willing/able to switch to ≤ 81 mg daily of acetylsalicylic acid or to another medication;
  14. Subjects requiring regular COX-2 inhibitor drug(s) or non-specific COX-1/COX-2 inhibiting drugs, or high dose steroids (excepting inhaled steroids); subjects may be enrolled if willing/able to undergo medication wash-out prior to the first dosing and to refrain from taking these drugs for the duration of the study;
  15. Have used an investigational drug within 30 days of Screening;
  16. Pregnant or currently lactating;
  17. Major psychiatric disorder in past 6 months;
  18. Known drug or alcohol dependence or any other factors which will interfere with the study conduct or interpretation of the results or who in the opinion of the Investigator are not suitable to participate.
- 

### **3.4. STUDY PROCEDURES**

---

Prior to recruitment of any subjects into the study, written approval of the protocol and informed consent must be obtained from the IRB and IBC (if applicable).

#### **3.4.1. INFORMED CONSENT**

---

The Investigator will explain the study purpose, procedures, and subject's responsibilities to the potential participant. The subject's willingness and ability to meet the follow-up requirements will be determined and written informed consent will be obtained ([Appendix 2](#)). The subject will sign and date the informed consent form. The Investigator will also sign and date the consent form. The original informed consent form will be retained with the subject records; a copy will be provided to the subject.

Following is a detailed list of study visits from screening to final follow-up and the required procedures/tests. Methodologies for specific tests/ procedures are described in [Section 0](#).

#### **3.4.2. SUBJECT IDENTIFICATION**

---

To maintain confidentiality, the subject's name should not be recorded on any study document other than the informed consent form. All subjects that give informed consent (sign the informed consent form) will be assigned a unique identifier in the following format: X-YY-ZZZ. X is the site number, YY is the sequential subject ID number, and ZZZ are the subject initials (initials of first name/middle name /last name) or Z-Z (initials of first and last name separated by hyphen, if no middle name). For example, the first subject named John Simon Doe at site 1 will be assigned 1-01-JSD; or if John doesn't have a middle name, it would be 1-01-J-D.

---

### **3.4.3. SCREENING (DAY -30 TO DAY 0)**

Prior to full screening, subjects will give informed consent. If applicable, the subject will be washed out of prohibited medication (see [section 3.4.4](#)). Subject eligibility will be assessed as follows:

- Evaluation of Eligibility Criteria
- Medical History
- Physical Exam
- Viral screening – HIV, Anti-Human T-Cell Lymphotropic Virus (HTLV), Active Hepatitis B or C as determined by Hepatitis B core antibody (HBcAb), antibody to Hepatitis B antigen (IgG and IgM; HBsAb), Hepatitis B surface antigen (HBsAg) and Hepatitis C antibodies (Anti-HCV)
- EKG
- Urine pregnancy test (for women of childbearing potential only)
- Concomitant Medications
- Vital Signs, including height
- Serum chemistry and hematology
- FVC
- ALSFRS-R

### **3.4.4. PROHIBITED CONCOMITANT MEDICATIONS**

#### **3.4.4.1. MEDICATION THAT MAY INTERFERE WITH VM202 BIOACTIVITY**

COX-1 and COX-2 inhibiting drugs may interfere with the bioactivity of VM202, and are therefore prohibited from use during the study. Other than the maximal 81 mg daily dose of aspirin (acetylsalicylic acid), subjects must agree to not take any of these drugs until completion of the 9 month follow-up visit. The patient needs to be advised that common over the counter medications that are prohibited include: Bayer (> 81mg), Excedrin, Aleve, Advil (motrin, ibuprofen). A more complete list of the excluded medications, including the washout period, can be found in [Appendix 3](#).

#### **3.4.4.2. SCREEN FAILURES**

Subjects not meeting all study entry criteria will be designated as a screen failures. End of study procedures will not be performed for these subjects, but their reason for discontinuation will be recorded on Screening Log. Screen failures will be replaced.

#### **3.4.5. TREATMENT AUTHORIZATION**

After providing written informed consent, potential study participants will undergo Screening assessments. The site will complete a Treatment Authorization Form (TAF) for subjects determined to be eligible for study participation. The TAF includes the subject identification number, demographic information (gender, date of birth), date of informed consent and indication that the subject meets all inclusion and exclusion criteria. The completed TAF will be faxed to the Sponsor or its designee. The Sponsor or its designee will confirm whether the subject can be treated and assign the Injection Schedule. Upon receipt, the Investigator or designee will

---

schedule the subject to undergo the study treatment. Note: adherence to this process is mandatory to track enrollment and to confirm initial treatment.

### **3.4.6. DAY 0 – 1ST INJECTION VISIT**

---

#### **3.4.6.1. PRE-INJECTION (≤ 24 HRS OF INJECTIONS)**

---

- FVC
- ALSFRS-R
- Muscle strength (MRC Scale)
- Muscle circumference
- Dynamometry

#### **3.4.6.2. PRE-INJECTION (≤ 4 HRS OF INJECTIONS)**

---

- Concomitant Medications
- Vital Signs
- Serum Chemistry and Hematology
- Serum HGF
- Copies of VM202 in whole blood

#### **3.4.6.3. 1ST DOSE OF VM202**

---

Patients receiving initial injection in the lower limbs will receive 38 injections (0.5 mL / each injection) in each leg as follows:

- Quadriceps - 20 injections/leg
- Calves – 12 injections/leg
- Tibialis anterior – 6 injections/leg

Patients receiving initial injection in the upper limbs will receive 26 injections (0.5 mL / each injection) in each arm as follows:

Hand:

- abductor pollicis brevis (APB) – 2 injections/hand
- first dorsal interosseous (FDI) – 2 injections/hand

Lower Arms:

- Extensor carpi radialis – 2 injection/arm
- Flexor carpi ulnaris – 2 injection/arm
- Flexor carpi radialis – 2 injection/arm

Upper Arms:

- Biceps – 8 injections/arm
- Deltoid – 8 injections/arm

#### **3.4.6.4. POST-INJECTION (1-3 HRS POST LAST INJECTION)**

---

- Vital Signs
- Copies of VM202 in whole blood (2 hours ± 1 hour post last injection)

- 
- Injection site assessment
  - Adverse event assessment

### **3.4.7. DAY 7 ± 1 DAY – 2ND INJECTION VISIT**

---

#### **3.4.7.1. PRE-INJECTION (≤ 4 HRS OF INJECTIONS)**

---

- Concomitant Medications
- Vital Signs
- Serum HGF
- Copies of VM202 in whole blood
- Injection site assessment
- Adverse event assessment

#### **3.4.7.2. 2ND DOSE OF VM202**

---

Patients that received injections in the upper limbs last injection visit (1st injection), will receive 38 injections (0.5 mL / each injection) in each leg as follows:

- Quadriceps - 20 injections/leg
- Calves – 12 injections/leg
- Tibialis anterior – 6 injections/leg

Patients that received injections in the lower limbs last injection visit (1st injection), will receive 26 injections (0.5 mL / each injection) in each arm as follows:

Hand:

- abductor pollicis brevis (APB) – 2 injections/hand
- first dorsal interosseous (FDI) – 2 injections/hand

Lower Arms:

- Extensor carpi radialis – 2 injection/arm
- Flexor carpi ulnaris – 2 injection/arm
- Flexor carpi radialis – 2 injection/arm

Upper Arms:

- Biceps – 8 injections/arm
- Deltoid – 8 injections/arm

#### **3.4.7.3. POST-INJECTION (1-3 HRS POST LAST INJECTION)**

---

- Vital Signs
- Copies of VM202 in whole blood (2 hours ± 1 hour post last injection)
- Injection site assessment
- Adverse event assessment

---

### **3.4.8. DAY 14 ± 1 DAY – 3RD INJECTION VISIT**

---

#### **3.4.8.1. PRE-INJECTION (≤ 4 HRS OF INJECTIONS)**

---

- Concomitant Medications
- Vital Signs
- Serum HGF
- Copies of VM202 in whole blood
- Injection site assessment
- Adverse event assessment

#### **3.4.8.2. 3RD DOSE OF VM202**

---

Patients that received injections in the upper limbs last injection visit (2nd injection), will receive 38 injections (0.5 mL / each injection) in each leg as follows:

- Quadriceps - 20 injections/leg
- Calves – 12 injections/leg
- Tibialis anterior – 6 injections/leg

Patients that received injections in the lower limbs last injection visit (2nd injection), will receive 26 injections (0.5 mL / each injection) in each arm as follows:

Hand:

- abductor pollicis brevis (APB) – 2 injections/hand
- first dorsal interosseous (FDI) – 2 injections/hand

Lower Arms:

- Extensor carpi radialis – 2 injection/arm
- Flexor carpi ulnaris – 2 injection/arm
- Flexor carpi radialis – 2 injection/arm

Upper Arms:

- Biceps – 8 injections/arm
- Deltoid – 8 injections/arm

#### **3.4.8.3. POST-INJECTION (1-3 HRS POST LAST INJECTION)**

---

- Vital Signs
- Copies of VM202 in whole blood (2 hours ± 1 hour post last injection)
- Injection site assessment
- Adverse event assessment

---

### **3.4.9. DAY 21 ± 1 DAY – 4TH INJECTION VISIT**

---

#### **3.4.9.1. PRE-INJECTION (≤ 4 HRS OF INJECTIONS)**

---

- Concomitant Medications
- Vital Signs

- 
- Serum HGF
  - Copies of VM202 in whole blood
  - Injection site assessment
  - Adverse event assessment

#### **3.4.9.2. 4TH DOSE OF VM202**

---

Patients that received injections in the upper limbs last injection visit (3rd injection), will receive 38 injections (0.5 mL / each injection) in each leg as follows:

- Quadriceps - 20 injections/leg
- Calves – 12 injections/leg
- Tibialis anterior – 6 injections/leg

Patients that received injections in the lower limbs last injection visit (3rd injection), will receive 26 injections (0.5 mL / each injection) in each arm as follows:

Hand:

- abductor pollicis brevis (APB) – 2 injections/hand
- first dorsal interosseous (FDI) – 2 injections/hand

Lower Arms:

- Extensor carpi radialis – 2 injection/arm
- Flexor carpi ulnaris – 2 injection/arm
- Flexor carpi radialis – 2 injection/arm

Upper Arms:

- Biceps – 8 injections/arm
- Deltoid – 8 injections/arm

#### **3.4.9.3. POST-INJECTION (1-3 HRS POST LAST INJECTION)**

---

- Vital Signs
- Copies of VM202 in whole blood (2 hours ± 1 hour post last injection)
- Injection site assessment
- Adverse event assessment

#### **3.4.10. DAY 30 ± 3 DAYS**

---

- Concomitant Medications
- Vital Signs
- Serum chemistry and hematology
- FVC
- ALSFRS-R
- Muscle strength (MRC scale)
- Serum HGF
- Copies of VM202 in whole blood
- Injection site assessment
- Adverse event assessment

---

#### **3.4.11. DAY 60 ± 3 DAYS**

---

- Concomitant Medications
- Vital Signs
- FVC
- ALSFRS-R
- Muscle strength (MRC Scale)
- Muscle circumference
- Dynamometry
- Serum HGF
- Copies of VM202 in whole blood
- Injection site assessment
- Adverse event assessment

#### **3.4.12. DAY 90 ± 7 DAYS**

---

- Concomitant Medications
- Vital Signs
- Serum chemistry and hematology
- FVC
- ALSFRS-R
- Muscle strength (MRC Scale)
- Muscle circumference
- Dynamometry
- Serum HGF
- Copies of VM202 in whole blood
- Adverse event assessment

#### **3.4.13. 6 MONTHS ± 1 MONTH**

---

- Concomitant Medications
- Vital Signs
- FVC
- ALSFRS-R
- Muscle strength (MRC Scale)
- Muscle circumference
- Dynamometry
- Adverse event assessment

#### **3.4.14. 9 MONTHS ± 1 MONTH**

---

- Physical exam
- EKG
- Concomitant Medications

- 
- Vital Signs
  - Serum chemistry and hematology
  - FVC
  - ALSFRS-R
  - Muscle strength (MRC Scale)
  - Muscle circumference
  - Dynamometry
  - Adverse event assessment

---

#### **3.4.15. MONTHS 12, 18, 24, 36 ± 1 MONTH**

---

- Phone call to assess survival
- 

### **3.5. STUDY COMPLETION**

---

#### **3.5.1. COMPLETED SUBJECTS**

---

Each subject in the study will undergo formal clinical assessments throughout the 9 Month Study follow-up visits. Patients will receive follow-up phone calls at 12, 18, 24, and 36 months to assess survival only.

#### **3.5.2. DISCONTINUED SUBJECTS**

---

Any subject may voluntarily discontinue the study at any time without prejudice. The Investigator may discontinue a subject from the study at any time if (s)he considers that remaining in the study compromises the subject's health or the subject is not sufficiently cooperative. In either event, reason(s) for discontinuation should be recorded on the CRF.

Possible reasons for study discontinuation include the following:

- Adverse events (AEs) necessitating discontinuation from the study (pre-treatment)
- The subject is lost to follow-up
- Subject decision
- Investigator decision
- Other reason

The reasons for any subject discontinuation will be specified and recorded on the study completion form of the CRF. Additional subjects may be enrolled if subjects discontinue prior to the 90 day visit.

Subjects discontinued for AE(s) will be followed-up after subject's discontinuation until the event is resolved or considered medically stable by the Investigator.

Subjects that withdraw prior to study completion will undergo the following assessments if possible:

- 
1. Concomitant Medications
  2. Vital signs
  3. Physical exam

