**SAFETY**

Adverse events (including serious adverse events, and adverse events leading to treatment discontinuation) throughout the 9 months follow-up will be described according to severity and to their relationship with the study drug and injection procedure. Descriptive statistics will be used to characterize safety parameters.

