#### 4.1.1. MEDICAL HISTORY

---

A medical history will be obtained at Screening/Baseline. All positive findings will be carefully documented on the CRF. Any new finding discovered during screening and prior to the first study drug administration (Day 0) will be considered to be part of the medical history and will not be recorded as an adverse event.

The Investigator will confirm the diagnosis of ALS using the revised El Escorial / Airlie House diagnostic criteria.

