### **5.1. DEFINITIONS**

---

An Adverse Event (AE) is the development of an untoward medical occurrence or the deterioration of a pre-existing medical condition following or during exposure to an investigational product, whether or not considered causally related to the product.

An untoward medical condition can be symptoms (*e.g.*, nausea, chest pain), signs (*e.g.*, tachycardia, enlarged liver) or clinically significant abnormal results of an investigation (*e.g.*, laboratory findings, electrocardiogram).

Conditions or diseases that are chronic but stable should not be recorded on AE pages of the CRF. In addition, changes in a chronic condition or disease that are consistent with natural disease progression are NOT considered AEs and also should not be recorded on AE pages of the CRF. These medical conditions should be adequately documented on the appropriate page of the CRF (medical history and/or physical examination).

An **adverse reaction** means any adverse event caused by a drug. Adverse reactions are a subset of all suspected adverse reactions for which there is reason to conclude that the drug caused the event.

**Suspected adverse reaction** means any adverse event for which there is a reasonable possibility that the drug caused the adverse event. For the purposes of IND safety reporting, ‘reasonable possibility’ means there is evidence to suggest a causal relationship between the drug and the adverse event. A suspected adverse reaction implies a lesser degree of certainty about causality than adverse reaction, which means any adverse event caused by a drug.

A **serious adverse event (SAE)** is any untoward medical occurrence which:

- Results in death;
- Is life-threatening;

- 
- Requires inpatient hospitalization (admission to hospital with a stay > 24 hours) or prolongation of hospitalization (note, elective procedures requiring hospitalization are not considered a SAE);
  - Results in permanent impairment of a body function or permanent damage to a body structure; or
  - Requires medical or surgical intervention to preclude permanent impairment of a body function or permanent damage to a body structure.

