### **5.3. REPORTING/RECORDING OF AEs**

---

Throughout the course of the study, all efforts will be made by the Investigator to remain alert to possible AEs. The first concern will be the safety of the subject, and

---

for providing appropriate medical intervention. The period of observation for collection of AEs starts during the first intramuscular injection procedure (Day 0) until the 9 month follow-up visit. Any AE should be recorded on the appropriate CRF page(s).

---

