### **6.2.1. SAFETY**

Any patient who receives VM202 will be included in the safety analysis population. Adverse events, serious adverse events, and adverse events leading to treatment discontinuation will be summarized using descriptive statistics. Categorical variables will be summarized by the number and percentage of patients in each category. Continuous variables will be summarized using n, mean, SD, median, minimum, and maximum values. No statistical testing will be performed.

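### Section 3.5.2 lists adverse events as a discontinuation reason only before treatment, when none can exist, so the 6.2.1 summary of AEs leading to treatment discontinuation has no defined source and could be under-counted

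*Combined protocol and SAP*

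**What the plan says.** Section 3.5.2 introduces its list with "Possible reasons for study discontinuation include the following". The first item is "Adverse events (AEs) necessitating discontinuation from the study (pre-treatment", after which the parenthesis closes. The other items are loss to follow-up, the subject's choice, the investigator's choice and a catch-all. The reasons are to be specified on the CRF's completion form. The same section later says that subjects discontinued for AEs are followed until the event resolves or is medically stable.

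The AE definitions point the other way from that first item:

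- Section 5.1 requires the event to occur "following or during exposure to an investigational product, whether or not considered causally related to the product".
- Section 5.3 sets the window: "The period of observation for collection of AEs starts during the first intramuscular injection procedure (Day 0) until the 9 month follow-up visit". Section 5.2 uses the same start and end.
- Section 4.1.1 says that a new finding made during screening and before the first dose "will be considered to be part of the medical history and will not be recorded as an adverse event".

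The analysis text is in section 6.2.1. On who is analysed: "Any patient who receives VM202 will be included in the safety analysis population". On what is reported: "Adverse events, serious adverse events, and adverse events leading to treatment discontinuation will be summarized using descriptive statistics". The Safety entry of the Synopsis also names "adverse events leading to treatment discontinuation".

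Section 6.1 classes as lost to follow-up any treated patient who does not complete the scheduled visits to 9 months.

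**The concern.** Safety and tolerability form the primary endpoint, and the course is demanding: four visits and 256 injections. Whether subjects stopped the course because of an adverse event is a question any reader of the report will ask, and the plan undertakes to answer it. Yet the only discontinuation reason that mentions AEs is confined to a period in which the protocol's own definitions rule AEs out.

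Suppose a subject reacts after the Day 0 or Day 7 injections and leaves the study. The listed reasons offer that subject a place only under a non-AE heading. If the subject stops injections but stays in follow-up, section 3.5.2 does not apply, because it deals with leaving the study. At stake is one descriptive line of the tolerability results, which could be lower than the truth without the reader being able to tell.

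**Working it through.** **1. Figure to reproduce.** There is none. The plan gives 18 subjects, no assumed discontinuation rate and no hypothesis test (sections 3.3 and 6). The check is mainly logical, and the arithmetic only shows scale.

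**2. The listed category against the definitions.**

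| Source | What it admits |
|---|---|
| 3.5.2, AE reason | AEs before treatment |
| 5.1, 5.2, 5.3 | AEs from the first injection onwards |
| 4.1.1 | Findings before the first dose are history, not AEs |
| 6.2.1 population | Subjects who received VM202 |

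The first row does not overlap with the second, and the third closes the gap between them. The AE reason in 3.5.2, read literally, therefore contains no treated subject.

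**3. Where an AE-driven stop after dosing would be recorded.**

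- *Subject leaves the study.* The remaining items in 3.5.2 are all non-AE reasons. Section 6.1 would also class the subject as lost to follow-up, since the visits to 9 months are not completed.
- *Subject stops injections but stays in follow-up.* Section 3.5.2 concerns study discontinuation only. No section defines treatment discontinuation or names a form for it.

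**4. Whether the AE form supplies the link.** Section 5.2 lists description, onset date, duration, frequency, severity, seriousness, treatment, outcome and relationship. Treatment most naturally means what was given for the event. No listed item says what was done with VM202 or whether the event led to stopping it. Drug accountability (3.6.2) gives the amount dispensed and the date, so a missed visit could be seen, but not the reason for it.

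**5. Size per subject.** With 18 treated: 1/18 = 5.6%, 2/18 = 11.1%, 3/18 = 16.7%. Section 3.5.2 lets additional subjects be enrolled when someone discontinues before Day 90. If each leaver is replaced, the figures become 1/19 = 5.3%, 2/20 = 10.0% and 3/21 = 14.3%. The counts 1 to 3 are illustrations; the documents give no expected number.

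**6. What a zero would mean.** A genuine 0/18 has an exact one-sided 95% upper limit of 1 − 0.05^(1/18) = 15.3% (two-sided: 1 − 0.025^(1/18) = 18.5%). The chance of a genuine zero is (1 − p)^18, where p is the true rate. These rates are assumptions, not taken from the documents:

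| Assumed p | P(0 of 18) | P(at least 1) |
|---|---|---|
| 2% | 69.5% | 30.5% |
| 5% | 39.7% | 60.3% |
| 10% | 15.0% | 85.0% |
| 20% | 1.8% | 98.2% |

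A zero that arose because AE-driven stops were filed elsewhere would support none of these limits, and it would look the same in the table.

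**The case against.** A reader might infer that the 6.2.1 summary must read zero by construction. The documents do not support that, for three reasons. The list in 3.5.2 is open: it gives possible reasons, ends with a catch-all and asks for the reason to be specified, so an AE could be written in. The CRF is not among the documents, so its actual categories are unknown. And the list concerns leaving the study, while 6.2.1 concerns stopping treatment; no text says that one feeds the other. All of this stands, so zero is possible but not certain.

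A reader might also infer that tolerability as a whole would go unmeasured, or that an AE-related stop could never be traced. Neither follows. AEs are to be described by severity and by relationship to drug and procedure. Injection sites are assessed repeatedly from Day 0 to Day 60 (4.2.11). AEs are assessed at early withdrawal, and a DSMB reviews the first six subjects. With 18 open-label subjects at one site, an AE followed by a missed injection visit might be pieced together from AE dates and dispensing records. The item list in 5.2 is also not stated to be exhaustive. This narrows the problem to one attribution line.

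The qualifier may have been meant as before the remaining injections, on Days 7 to 21. Nothing in the text says so, and the ambiguity is itself a reason to clarify.

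The sentence on following up subjects discontinued for AEs shows that such cases were expected and must be identifiable. It does not resolve the conflict, because it contradicts the listed reason a few lines above it. Recovery from free text is not a defined source for a pre-specified summary. No decision rule uses this count, which limits the consequence but does not make the line accurate.

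**Conclusion.** The point holds as an internal contradiction and a missing data source. The AE reason in 3.5.2 is empty for all treated subjects under 4.1.1, 5.1, 5.2 and 5.3. It conflicts with the same section's follow-up sentence and leaves the promised 6.2.1 line without a listed item to supply it. Applied literally, the wording moves AE-driven stops into non-AE categories, so any error from this misfiling is an under-count, worth 5.6 percentage points per subject when 18 are treated.

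This rests on two assumptions: that the CRF follows the lists in 3.5.2 and 5.2, and that at least one subject stops because of an AE after dosing. Neither can be settled from the documents. The consequence is confined to one descriptive tolerability line; it does not put the whole safety assessment in doubt. It is worth correcting before enrolment, because a reason not captured at the time may not be recoverable.

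**What to change.** Reconcile sections 3.5.2, 4.1.1, 5.1, 5.2, 5.3, 6.1 and 6.2.1. On the recording side:

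1. Remove the pre-treatment qualifier from the AE reason in 3.5.2, so that an AE can be recorded as the reason after dosing.
2. Add an item to the AE form for the action taken with VM202 and whether the event led to discontinuation.
3. Record stopping the injection series separately from leaving the study, and name these items in 6.2.1 as the source of the summary.
4. Adjust 6.1 so that a treated subject who leaves for a known AE is not classed as lost to follow-up.

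The cost is minor protocol wording and a few CRF fields, with no new visits. The tolerability figure may come out less favourable. When treatment should be stopped is a clinical matter for the sponsor and investigator, and nothing is proposed on it here.
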